Procedures at Visit 5 of study IA/PAAG-SI/OA/2019 (hereinafter referred to in the Protocol as Clinical study 1 - CS1) that coincide with the screening Visit procedures (Visit 0) in study IA/PAAG-SI/OA/2020 will be counted as the procedures of Visit 0 of study IA/PAAG-SI/OA/2020, there is no need to repeat the identical procedures of these visits.

- The signing of the informed consent;
- The collection of demographic data;
- Measurement of the body weight;
- Collection of complaints and anamnesis;
- Registration of concomitant therapy;
- Assessment of the main vital signs (blood pressure [BP], heart rate [HR], number of respiratory movements [RR], body temperature);
- Physical examination of joints;

- Completing an algofunctional questionnaire for evaluating the osteoarthritis index developed by researchers at the Western Ontario and McMaster Universities Osteoarthritis, WOMAC with an assessment of subscale pain (WOMAC-A), stiffness (WOMAC-B), and functional performance (WOMAC-C) (from *Visit 5 of CS1*);
- Assessment of the severity of pain in the target knee joint by 100-mm VAS (from *Visit 5 of CS1*);
- Evaluation of the effectiveness of treatment by the patient, parameter OEP (from *Visit 5 of CS1*);
- Evaluation of the effectiveness of treatment by the investigator, parameter OEI (from *Visit* 5 of CS1);
- Documenting the target knee joint (the same joint that was identified as the target in the IA/PAAG-SI/OA/2019 study);
- Clinical blood test (hemoglobin level, hematocrit, red blood cell count, white blood cell count, white blood cell formula, platelet count, ESR) (from *Visit 5 of CS1*);
- Biochemical analysis of blood (glucose, alanine aminotransferase [SPGT], aspartate aminotransferase [AST], alkaline phosphatase [ALP], gamma-glutamyltranspeptidase [GGTP], total bilirubin, creatinine, uric acid, rheumatoid factor) (from *Visit 5 of CS1*);
- Coagulogram (APTT, PT, prothrombin index, fibrinogen) (from *Visit 5 of CS1*);
- Blood tests for antibodies to human immunodeficiency virus (HIV), hepatitis b surface antigen (HBsAg) and antibodies to Hepatitis C Virus (anti-HCV]), syphilis (RW);
- General urinalysis (color, transparency, relative density, pH, glucose, protein, ketone bodies, urobilinogen) (from *Visit 5 of CS1*);
- Rapid urine test for pregnancy in women with preserved reproductive potential (from *Visit* 5 of CS1);
- Evaluation of inclusion/non-inclusion criteria;
- Issuing a patient's diary;
- Check AE and serious AE (SAE).

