#### **3.1.3.** Analysis of efficacy parameters

Main efficacy parameters of the studied MD:

1. Change in the overall score on the WOMAC scale (WOMAC-T) on Visit 3 (week 13), Visit 5 (week 25) compared to the basal value on Visit 0 (screening) of the open study and compared to the basal value on Visit 1 (week 1) of the IA/PAAG-SI/OA/2019 study;

2. Change in the pain subscale score (WOMAC-A) on Visit 3 (week 13), Visit 5 (week 25) compared to the basal value on Visit 0 (screening) of the open study and compared to the basal value on Visit 1 (week 1) of the IA/PAAG-SI/OA/2019 study;

3. Change in the score for stiffness subscale (WOMAC-B) and functional performance (WOMAC-C) at Visit 3 (week 13), Visit 5 (week 25) compared to the basal value at Visit 0 (screening) of open study and compared to the basal value at Visit 1 (week 1) of the study IA/PAAG-SI/OA/2019;

4. The change in the severity of pain in the target knee on a 100-mm VAS at Visit 2 (week 1), Visit 3 (week 13), Visit 5 (week 25) compared to the basal value at Visit 0 (screening) of open safety study and compared to the basal value at Visit 1 (week 1) study IA/PAAG-SI/OA/2019;

5. Evaluation of the effectiveness of treatment by the patient, parameter OEP (on a scale from 1-clear deterioration to 6-significant improvement) on Visits 3 and 5 (parameters OEP-w13 and OEP-w25, respectively);

6. Evaluation of the effectiveness of treatment by the investigator, parameter OEI (on a scale from 1-clear deterioration to 6-significant improvement) on Visits 3 and 5 (parameters OEI-w13, OEI-w25, respectively);

7. Assessment of the total number of paracetamol tablets taken (one tablet = 500 mg) starting from day 1 on Visits 3 and 5 (PARACETAMOL -w13 and PARACETAMOL-w25, respectively);

8. Assessment of the total number of NSAID tablets taken starting from day 1 on Visits 3 and 5 (NSAID-w13 and NSAID-w25, respectively);

9. The parameter JSN of the target knee joint at Visit 5 of the open study compared to the basal value on Visit 0 of the IA/PAAG-SI/OA/2019 study retrospectively.

All performance parameters will be analyzed both among all patients included in open study no. IA/PAAG-SI/OA/2020 (using descriptive statistics) and in subgroups of patients:

- those who received only one course of injections in the placebo-controlled study IA/PAAG-SI/OA/2019;
- those who received two courses of therapy both in the placebo-controlled and at Visit 1 (and as per the indications at Visit 2) of the open study;

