- those who received two courses of therapy both in the placebo-controlled and at Visit 3
  (and as per the indications at Visit 4) of the open study.

For comparison between these subgroups, variance analysis will be used (for quantitative parameters other than those based on WOMAC), covariance analysis (for quantitative parameters based on WOMAC, in this case the initial value of WOMAC in the double-blind phase of the study will be used as a covariate, and the results will be presented as the average, calculated by the least squares method), or the "Chi-square" criterion (for qualitative parameters), followed by the application of multiple comparison criteria (if necessary).

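### The week-25 subgroup comparisons of the patient and investigator effectiveness ratings (OEP, OEI) ignore the Visit 0 rating, so a difference present before re-injection can appear as one between single and repeated course

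*SAP*

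**What the plan says.** The Protocol's Visit 0 procedures include "Evaluation of the effectiveness of treatment by the patient, parameter OEP" and "Evaluation of the effectiveness of treatment by the investigator, parameter OEI". Both values are carried over from Visit 5 of the first study (IA/PAAG-SI/OA/2019).

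SAP 3.1.3, items 5 and 6, defines the endpoints as the ratings themselves: "parameter OEP (on a scale from 1-clear deterioration to 6-significant improvement) on Visits 3 and 5" and "parameter OEI (on a scale from 1-clear deterioration to 6-significant improvement) on Visits 3 and 5". Items 1 to 4 (WOMAC and VAS) are defined as changes from Visit 0 of the open study and from the first study's baseline.

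For comparisons between subgroups, SAP 3.1.3 says "variance analysis will be used (for quantitative parameters other than those based on WOMAC". For WOMAC endpoints, "the initial value of WOMAC in the double-blind phase of the study will be used as a covariate". Qualitative parameters go to a chi-square test. SAP 3.1 counts ordinal data as qualitative, so OEP and OEI probably go to chi-square. Neither chi-square nor analysis of variance, as planned, uses a covariate.

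Three subgroups are compared: first course only, second course from Visit 1, and second course from Visit 3. Under the Protocol's study design, Group A (pain reduced by less than 40% since the first study's Visit 1) is injected at Visit 1. Group B (reduced by 40% or more, or re-injection not possible) is not. Group B is split again at Visit 3 on pain at that visit. SAP 3.6 itself says the subgroups follow actual need for treatment.

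**The concern.** Patients are sorted at entry on how well the first course worked. The Visit 0 OEP and OEI judge that same course at that same time. Group A should therefore tend to enter with lower ratings than Group B.

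If a patient's ratings are correlated over time, part of that gap will still be present at week 25 even if re-injection does nothing. The planned test would show it as a difference between patients with one course and patients with two. The likely direction is against the early repeated course: it could look ineffective, or a real benefit could be hidden. Two planned week-25 comparisons are affected, OEP-w25 and OEI-w25. Both are listed among the main efficacy parameters and tested at 5% (SAP 3.4).

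SAP 3.1.1 plans a comparison of initial characteristics across the same three subgroups. It does not name OEP or OEI. It might display a Visit 0 gap, but it would not adjust the week-25 result for it.

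**Working it through.** **Inputs from the documents.** At most 72 patients, with no sample size calculation (SAP 3.3); two-sided 5% level (SAP 3.4). There is no power, SD, correlation or subgroup size to reproduce.

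**Assumptions.** Subgroup sizes 36 v 36 or 24 v 48; Visit 0 gap d of 0.5, 1.0 or 1.5 SD; within-subgroup correlation rho between the Visit 0 and week-25 ratings of 0.3, 0.5 or 0.7; equal SDs at both visits; no effect of re-injection.

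**1. Carry-over bias.** The expected week-25 difference is rho × d, in SD units. With SE = sqrt(1/n1 + 1/n2), the rejection rate is Phi(rho·d/SE − 1.96) + Phi(−rho·d/SE − 1.96).

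For rho = 0.5, d = 1 and 36 v 36: the bias is 0.5 SD and SE = sqrt(2/36) = 0.236. Then 0.5/0.236 = 2.12, and Phi(2.12 − 1.96) = Phi(0.16), about 0.56. For 24 v 48: SE = 0.25, 0.5/0.25 = 2.00, and Phi(0.04) is about 0.52.

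| rho | d | bias (SD) | rejection, 36 v 36 | rejection, 24 v 48 |
|---|---|---|---|---|
| 0.3 | 0.5 | 0.15 | 9.8% | 9.2% |
| 0.3 | 1.0 | 0.30 | 24.7% | 22.4% |
| 0.3 | 1.5 | 0.45 | 48.0% | 43.7% |
| 0.5 | 0.5 | 0.25 | 18.6% | 17.0% |
| 0.5 | 1.0 | 0.50 | 56.4% | 51.6% |
| 0.5 | 1.5 | 0.75 | 88.9% | 85.1% |
| 0.7 | 0.5 | 0.35 | 31.8% | 28.8% |
| 0.7 | 1.0 | 0.70 | 84.4% | 80.0% |
| 0.7 | 1.5 | 1.05 | 99.4% | 98.7% |

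**2. Effect of adjustment on precision.** Var(adjusted)/Var(unadjusted) is about (1 − rho²)(1 + d²·p(1 − p)), where p is the share in one subgroup. The second factor is the price of a covariate that differs between subgroups. For p = 0.5:

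| d | rho 0.3 | rho 0.5 | rho 0.7 |
|---|---|---|---|
| 0 | 0.91 | 0.75 | 0.51 |
| 1.0 | 1.14 | 0.94 | 0.64 |
| 1.5 | 1.42 | 1.17 | 0.80 |

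Example: d = 1, rho = 0.5 gives 0.75 × 1.25 = 0.94. A ratio above 1 means that adjustment widens the standard error.

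**3. Simulation with three subgroups.** Setting: 72 patients, six-category ratings, subgroups cut at the median of pain response at Visit 0 and again at Visit 3, no re-injection effect, nine scenarios of up to 1,500 runs each. The rating–pain correlation is 0.4 to 0.8 and the visit-to-visit correlation 0.3 to 0.7, so the Visit 0 to week-25 correlation is 0.09 to 0.49 (the squares).

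- Week 25, three-subgroup rejection: chi-square 5 to 58%; analysis of variance 8.5 to 86%; covariance analysis on the Visit 0 rating 7 to 36%.
- Week 25, Group A v Group B gap: 0.10 to 1.03 rating points unadjusted, 0.01 to 0.05 adjusted. The variance ratio is 0.92 to 1.81, below 1 in one of nine scenarios.
- Week 13, three-subgroup rejection: analysis of variance 41 to 99.9%; covariance analysis 24 to 97%.

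The near-complete removal of the A v B gap is partly built in. In this model the Visit 0 to week-25 pain–rating correlation equals the product of the pain–rating correlation at Visit 0 and the Visit 0 to week-25 rating correlation. Pain at entry therefore adds nothing once the Visit 0 rating is known. A separate simulation (72 patients, two equal subgroups, 2,000 runs) let first-course response load on a stable patient component as well. It left an adjusted gap of 0.0 to 0.55 points, from 0.6 to 1.2 unadjusted.

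**The case against.** **The Visit 0 value is not an ordinary baseline.** OEP and OEI run from deterioration to improvement, so they already express change. The Visit 0 value judges the first course, and the documents do not say what the ratings at Visits 3 and 5 are measured against. This stands as a reason not to subtract one rating from another, and it weakens the contrast with WOMAC and VAS, which measure state. It does not remove the bias: a prior rating tied to subgroup membership can still predict the later rating.

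**Other endpoints are also raw.** Paracetamol and NSAID totals are analysed without a baseline. This is true, but they are counted from Day 1 and have no Visit 0 value listed for use. OEP and OEI do.

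**Adjustment cannot make the comparison causal.** This stands. It also cannot repair week 13. The late re-injection subgroup is chosen on pain at Visit 3, the visit at which OEP-w13 and OEI-w13 are recorded, and its first open-study injection is given at that visit. Some of the same selection remains in the three-subgroup comparison at week 25.

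**Safety is the main aim.** Overall efficacy is descriptive, and no passage says that subgroup differences will be read as effects of repeating the course. Both are true and they limit the weight of the point. The plan nevertheless tests these differences at 5%, with no caution on interpretation in SAP 3.1.3.

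**A stronger inference.** A reader might infer that ignoring the Visit 0 rating also wastes precision and power, by the factor 1 − rho² (0.75 at rho = 0.5). That factor needs a covariate balanced between subgroups, as under randomisation. Here the imbalance is the reason for concern, and the second table shows that the standard error may widen.

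**Conclusion.** The point holds as a matter of bias at week 25. The Visit 0 ratings exist, the planned tests of OEP-w25 and OEI-w25 leave them out, and the subgroups are formed mainly on a closely related response at entry.

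The size is illustrative. A 1 SD Visit 0 gap and a correlation of 0.5 give a spurious 0.5 SD difference and about 56% rejection at 36 v 36. Over the assumed range, rejection runs from 9% to 99%. The planned chi-square test gave 5 to 58% in the three-subgroup simulation, so in the mildest scenarios the harm is negligible. Every correlation, gap and subgroup size is assumed. The real gap may be smaller, because Group B also takes patients who responded poorly but cannot be re-injected. Fewer than 72 patients would lower the rejection rate but not the bias.

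No gain in precision or power can be claimed, and Visit 0 adjustment does not make the week-13 comparisons sound. The point concerns secondary subgroup tests in a study whose main purpose is safety.

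**What to change.** In SAP 3.1.3:

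- For OEP-w25 and OEI-w25, add a subgroup comparison adjusted for the patient's own Visit 0 rating, for example an ordinal logistic model with subgroup and Visit 0 rating. At the least, make it a sensitivity analysis beside the planned test.
- Report the Visit 0 distribution of OEP and OEI by subgroup, naming both in SAP 3.1.1.
- For OEP-w13 and OEI-w13, report by subgroup descriptively, because of the selection on Visit 3 pain.
- State that these subgroup comparisons are non-causal.

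Cost: a few sentences and one further model for each rating, with no new data collection. Intervals may be wider and some bias will remain. Patients without a Visit 0 rating drop out of the model, since SAP 3.6 rules out imputation. They should be few, because inclusion criterion 5 requires completion of the first study through Visit 5, from which the rating is taken.

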At Visit 3 additional evaluation will be conducted to assess the feasibility and possibility of reinjections with MD NOLTREXTM among patients of group B. If at Visit 3 of the open study pain remains the same in the target joint of the study IA/PAAG-SI/OA/2019 or increases in intensity (as per 100-mm VAS) in comparison with the assessment at Visit 1 of the study IA/PAAG-SI/OA/2019 (or if a decrease in pain severity is less than 40% when compared to the rating at Visit 1 of the study IA/PAAG-SI/OA/2019), in the absence of the above criteria for non-treatment with the studied MD, at Visit 3 of open study the injection of MD NOLTREXTM into the target knee joint will be performed. MD will be administered in accordance with the instructions for medical use of MD NOLTREXTM: 4.0 ml per injection (2.5 + 1.5 ml, or 2.0 + 2.0 ml from two syringes through one needle [one puncture]) once or twice at intervals of one week. The treatment course in the framework of an open study among patients of Group B is a maximum of 2 injections (the first - at Visit 3, the second - at Visit 4). The number of injections is determined by the doctor depending on the stage of gonarthrosis and the clinical response. In order to avoid overfilling the joint with dense slowly resorbable material, at the good clinical result (reducing the pain severity on a 100 mm VAS by Visit 2 by more than 40— compared to the basal level in the open study[1]), the course of injections will be discontinued. The open nature of the study in one group is determined by the main purpose of the study - to assess the safety of MD NOLTREX[™] with a single or repeated course of use. Placebo safety data at the 6-month point (visit 5) in the IA/PAAG-SI/OA/2019 study will be used as a control. It is assumed that continued monitoring of patients in the placebo group will not lead to the detection of new adverse events (AE), the frequency of which should be compared with the frequency in the active therapy group, and is connected to unethical restriction of patients in the placebo group in the possibility of using potentially effective synovial fluid endoprostheses.

The open study provides follow-up of patients for 6 months (up to 25 weeks from Visit 1).

Thus, the maximum duration of participation in the study for one patient will be a maximum of 172 days.

Patient visits

Visit 0 (Day 0, -24 h -0 h, screening)

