Visit 1 (Week 0, Day 1, start of treatment)

- Measurement of the body weight;
- Collection of complaints and anamnesis;
- Registration of concomitant therapy;

- Assessment of the main vital signs (BP, HR, RR, body temperature);
- Physical examination of joints;
- Evaluation of inclusion/non-inclusion criteria;
- Injection of the studies MD into the cavity of the target joint (only for group A patients who are shown to receive the injection in accordance with the criteria specified in the Protocol);
- Registration of AE and SAE;
- Evaluation of exclusion criteria.

Every 2 weeks between Visit 1 and Visit 3 (weeks 3, 5, 7, 9 and 11), telephone contacts are made with the patient to clarify complaints, AE and the need for taking paracetamol or NSAIDs for the past 2 weeks. If AE is detected, or the need to take paracetamol or NSAIDs more than 4 days a week in each of the consecutive 2 weeks, the patient is invited to the clinic for an unscheduled Visit or a Visit to prematurely complete participation in the study (depending on the reason for the visit).

Visit 2 (Week 1, Day 8, treatment and follow-up) - as indicated

Only patients who received an injection of MD NOLTREXTM into the target knee joint on Visit 1 are eligible for Visit 2.

The following procedures must be performed during the visit:

- Measurement of the body weight;
- Collection of complaints and anamnesis;
- Registration of concomitant therapy;
- Assessment of the main vital signs (BP, HR, RR, body temperature);
- Physical examination of joints;
- Assessment of the severity of pain in the target knee joint using 100-mm VAS;
- Injection of the studied MD into the target joint cavity (only for patients of group A, in which the severity of pain in the target knee joint using 100 mm VAS did not decrease by 40% or more compared to the assessment on the Visit 0);
- Evaluation of the patient's diary;
- Return of the diary to the patient;
- Registration of AE and SAE;
- Evaluation of exclusion criteria.

Visit 3 (Week 13, Day 84 ± 2, treatment and follow-up)

- Measurement of the body weight;
- Collection of complaints and anamnesis;
- Registration of concomitant therapy;
- Assessment of the main vital signs (BP, HR, RR, body temperature);
- Physical examination of joints;
- Filling out algofunctional questionnaire WOMAC with an assessment of the subscales of pain (WOMAC-A), stiffness (WOMAC-B) and functional performance (WOMAC-C);

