- Assessment of the severity of pain in the target knee joint using 100-mm VAS;
- Evaluation of the effectiveness of treatment by the patient, OEP parameter;
- Evaluation of the effectiveness of treatment by the investigator, OEI parameter;
- Clinical blood test (hemoglobin level, hematocrit, red blood cell count, white blood cell formula, platelet count, ESR);
- Biochemical blood test (glucose, ALT, AST, ALP, GGTP, total bilirubin, creatinine, uric acid, rheumatoid factor);
- Coagulogram (APTT, PT, prothrombin index, fibrinogen)
- General urinalysis (color, transparency, relative density, pH, glucose, protein, ketone bodies, urobilinogen);
- Injection of the studied MD into the cavity of the target joint (only for patients of Group B who are shown to receive the injection according to the criteria specified in the Protocol, and didn't receive the injection at Visit 1);
- Evaluation of the patient's diary;
- Evaluation of the total number of paracetamol tablets taken (one tablet = 500 mg) using patient's diary, PARACETAMOL parameter;
- Evaluation of the patient's diary of the total number of NSAIDs allowed by the Protocol in case of paracetamol inefficiency (NSAIDs allowed by the Protocol in case of paracetamol inefficiency: diclofenac potassium tablets 50 mg, diclofenac sodium tablets 75 mg, naproxen tablets 500 mg, naproxen sodium tablets 550 mg, meloxicam tablets 7.5 mg, celecoxib tablets 200 mg), NSAID parameter;
- Issuing a new patient diary to the patient;
- Registration of AE and SAE;
- Evaluation of exclusion criteria.

Every 2 weeks, between Visit 3 and Visit 4 (weeks 15, 17, 19, 21 and 23), telephone contacts are made with the patient to clarify complaints, AE and the need for taking paracetamol or NSAIDs for the past 2 weeks. If AE is detected, or the need to take paracetamol or NSAIDs more than 4 days a

week in each of the consecutive 2 weeks, the patient is invited to the clinic for an unscheduled Visit or a Visit to prematurely complete participation in the study (depending on the reason for the visit).

Visit 4 (Week 14, Day 91 ± 2, treatment and follow-up) - as indicated

Only patients who received an injection of MD NOLTREXTM into the target knee joint on Visit 3 are eligible for Visit 4.

The following procedures must be performed during the visit:

- Measurement of the body weight;
- Collection of complaints and anamnesis;
- Registration of concomitant therapy;
- Assessment of the main vital signs (BP, HR, RR, body temperature);

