- Physical examination of joints;
- Assessment of the severity of pain in the target knee joint using 100-mm VAS;
- Injection of the studied MD into the target joint cavity (only for patients of Group B, in which the severity of pain in the target knee joint using 100 mm VAS did not decrease by 40% or more compared to the assessment at Visit 3)
- Evaluation of the patient's diary;
- Return of the diary to the patient;
- Registration of AE and SAE;
- Evaluation of exclusion criteria.

Visit 5 (Week 25, Day 169 ± 2 , follow-up)

- Measurement of the body weight;
- Collection of complaints and anamnesis;
- Registration of concomitant therapy;
- Assessment of the main vital signs (BP, HR, RR, body temperature);
- Physical examination of joints;
- Radiography of the knee joints and documentation of parameters of joint space width (JSW) and joint space narrowing (JSN);
- Filling out algofunctional questionnaire WOMAC with an assessment of the subscales of pain (WOMAC-A), stiffness (WOMAC-B) and functional performance (WOMAC-C);

- Assessment of the severity of pain in the target knee joint using 100-mm VAS;
- Evaluation of the effectiveness of treatment by the patient, OEP parameter;
- Evaluation of the effectiveness of treatment by the investigator, OEI parameter;
- Clinical blood test (hemoglobin level, hematocrit, red blood cell count, white blood cell formula, platelet count, ESR);
- Biochemical blood test (glucose, ALT, AST, ALP, GGTP, total bilirubin, creatinine, uric acid, rheumatoid factor);
- Coagulogram (APTT, PT, prothrombin index, fibrinogen);
- General urinalysis (color, transparency, relative density, pH, glucose, protein, ketone bodies, urobilinogen);
- Evaluation of the patient's diary;
- Evaluation of the total number of paracetamol tablets taken (one tablet = 500 mg) using patient's diary, PARACETAMOL parameter;
- As per patient's diary, evaluation of the total number of NSAIDs allowed by the Protocol in case of paracetamol inefficiency (NSAIDs allowed by the Protocol in case of paracetamol inefficiency: diclofenac potassium tablets 50 mg, diclofenac sodium tablets 75 mg, naproxen tablets 500 mg, naproxen sodium tablets 550 mg, meloxicam tablets 7.5 mg, celecoxib tablets 200 mg), NSAID parameter;
- Registration of AE and SAE;
- Evaluation of exclusion criteria.

An unscheduled visit

The following procedures must be performed during the visit:

- Measurement of the body weight
- Collection of complaints and anamnesis;

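### The Visit 5 tablet totals run from Day 1, so about half of the counted period precedes the injection in the Visit 3 subgroup and none of it does in the Visit 1 subgroup

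*SAP*

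**What the plan says.** SAP 3.1.3, items 7 and 8, defines the analgesic parameters as "Assessment of the total number of paracetamol tablets taken (one tablet = 500 mg) starting from day 1 on Visits 3 and 5" and "Assessment of the total number of NSAID tablets taken starting from day 1 on Visits 3 and 5". SAP section 2 and the Protocol's list of main effectiveness parameters carry the same definitions. The count starts at "Visit 1 (Week 0, Day 1, start of treatment" and is read at "Visit 3 (Week 13, Day 84 ± 2, treatment and follow-up" and at "Visit 5 (Week 25, Day 169" (± 2 days).

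All efficacy parameters are described in all patients and in three subgroups: no course in the open study, a course starting at Visit 1, and a course starting at Visit 3. For Group B the open-study injections are scheduled as "the first - at Visit 3, the second - at Visit 4". SAP 3.1.3 compares the subgroups by analysis of variance for quantitative parameters not based on WOMAC. Only the WOMAC parameters get a covariate.

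The Visit 3 procedures include "Issuing a new patient diary to the patient". Neither document defines a Visit 3 to Visit 5 total, a w25-minus-w13 difference or a tablets-per-day rate.

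**The concern.** The second task of the Protocol is to evaluate the effect of the device on knee function and on the need for paracetamol and NSAIDs. The tablet totals are the planned measures of that need, and SAP 1.1.2 cites them as objective evidence in an open study.

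A total from Day 1 means different things in different subgroups. In the Visit 1 subgroup, every tablet in the w25 total was taken after the open-study injection. In the Visit 3 subgroup, tablets from the first 83 days were taken before it and cannot reflect it, yet they enter the same number and the same test. The w25 total also contains the w13 total, so in every subgroup the Visit 5 result partly repeats the Visit 3 result.

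WOMAC, VAS and the patient and investigator ratings are assessed at each visit, so they do not carry earlier tablets forward in this way. The problem is specific to the cumulative counts.

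**Working it through.** The plan gives no tablet rate, effect size or power for these parameters, so it has no figure of its own to reproduce.

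**Inputs (Protocol visit schedule).** Count starts on Day 1. Visit 3 is Day 84 (82 to 86). Visit 4, "Visit 4 (Week 14, Day 91 ± 2, treatment and follow-up", is Day 91. Visit 5 is Day 169 (167 to 171).

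**Share of the period before the Visit 3 injection.**
- Before: 84 − 1 = 83 days. After: 169 − 84 = 85 days. Total: 168 days.
- 83/168 = 49.4%.
- Across the windows: 81/170 = 47.6% (Visit 3 on Day 82, Visit 5 on Day 171) to 85/166 = 51.2% (Day 86, Day 167).
- Visit 1 subgroup: 0 of 168 days.

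**Dilution.** Let *e* be the true reduction after Visit 3, and *r* the untreated tablet rate after Visit 3 divided by the rate before it. Relative to the total expected without re-injection:

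apparent reduction = *e* × *r* × 85 / (83 + *r* × 85)

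For a true halving (*e* = 0.5):

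| *r* (assumed) | Calculation | Apparent reduction |
|---|---|---|
| 0.5 | 21.25 / 125.5 | 16.9% |
| 0.75 | 31.875 / 146.75 | 21.7% |
| 1 | 42.5 / 168 | 25.3% |
| 1.5 | 63.75 / 210.5 | 30.3% |
| 2 | 85 / 253 | 33.6% |

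**Sensitivity to the dates, with *r* = 1.**
- Visit windows: 24.4% to 26.2%.
- Effect starting only at the Visit 4 injection: 90/168 = 53.6% of days come before, and the apparent reduction is 0.5 × 78/168 = 23.2%.
- Week labels 13 and 25 in place of days: 13/25 = 52%, and 24.0%. The week and day labels do not match fully, but this does not change the result.

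**Check that a separate period recovers the effect.** Take one tablet a day before Visit 3 and half a tablet a day after it. Then w13 = 83 and w25 = 83 + 42.5 = 125.5. The cumulative total shows 1 − 125.5/168 = 25.3%. The difference w25 − w13 = 42.5, against 85 expected without an effect, shows the full 50%.

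**The case against.** Four points on the other side deserve weight.

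1. *No planned table would show the 25%.* This stands. Items 7 and 8 are raw totals with no baseline and no percent change. A reader might infer that the report will state a halving as a 25% reduction, but the documents do not plan that. The figure is relative to an unobserved no-injection total and only measures how far the signal is weakened. The defect lies in the subgroup description and the between-subgroup analysis of variance.

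2. *The first-period tablets are not all relapse tablets.* This also stands. A reader might infer that Visit 3 recipients are patients whose pain had come back. Group B, however, combines patients whose pain was down by 40% or more at entry with patients who could not be re-injected then. The first group may have used few tablets for much of the first period, which makes *r* above 1 plausible; the second may never have responded. This is why a range is shown. The dilution remains throughout it.

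3. *Nothing is lost.* Correct: w25 minus w13 can be derived from planned data. But in an open study, a measure chosen after the data are seen is a post hoc choice.

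4. *Sites might count only the new diary at Visit 5.* The Visit 5 procedure refers only to the patient's diary, so this could happen. The parameter definition says from Day 1, so the cumulative reading is the plain one. The possibility is a further reason to define each period.

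The impact is limited in any case: safety is the main purpose, no sample size was calculated, and the subgroups are formed by need for treatment.

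**Conclusion.** The concern holds in this form. The day counts come from the documents alone: about half of the w25 period (49.4%; 47.6% to 51.2%) precedes the first open-study injection in the Visit 3 subgroup, against none in the Visit 1 subgroup, and nothing in either document re-anchors the count. The Visit 5 comparison between these subgroups is not like-for-like, and any effect of the Visit 3 course is diluted in it.

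The size of the dilution rests on an assumption. A true halving would show as about 25% with a constant untreated rate, and as about 17% to 34% with an untreated rate ratio of 0.5 to 2.

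It does not follow that the cumulative total is wrong for everyone or should be replaced. For the Visit 1 subgroup, Day 1 to Visit 5 is the period since injection, and a second-period total alone would drop its first 83 days after injection.

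**What to change.** Keep the cumulative w25 totals. In SAP 3.1.3, items 7 and 8, prespecify for each subgroup a separate Visit 3 to Visit 5 total (w25 minus w13, from the diary issued at Visit 3), or tablets per day since the latest open-study injection. The rate is undefined for patients with no open-study injection, so the period total is simpler to apply to all three subgroups.

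Use this measure to describe the Visit 3 course, and report it in the Visit 5 subgroup comparison alongside the cumulative total. State the time since injection for each subgroup: from Visit 3 to Visit 5, the Visit 1 subgroup is already about 83 days past its first injection.

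Any comparison with the patient's own first period should be descriptive only, with two cautions. Patients are injected because of their pain at Visit 3, so regression to the mean can favour the device. Low tablet use during an earlier response can make an effective course look harmful.

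Cost: no new data or visits, and a small addition to the SAP, to be recorded in the final report under SAP 3.7. If the parameter list itself is changed, SAP section 2 and the Protocol's list of main effectiveness parameters need matching wording. The Protocol change would then go through the amendment approvals in SAP section 5.
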